NOTE: In addition to the adverse event reporting requirements of the sponsor, the principal investigator must follow the Partners Human Research Committee guidelines for Adverse Event Reporting

The Principal Investigator assumes responsibility for ensuring informed consent, data management, and the detection and reporting of adverse events. In general, the data to be reviewed will include screening data, baseline data, efficacy data, safety data, quality assurance data, accrual status including projections, and any other data that will help in the assessment of the effectiveness of the clinical trial.

The risk associated with participating in this study is moderate. D-cycloserine has been established as a safe treatment for tuberculosis. Consequently, serious side effects associated with this treatment are not expected. There will be on-call medical coverage to respond to any adverse events throughout the clinical trial.

The Principal Investigator will conduct a review of all adverse events and determine the attribution and grade of severity of the adverse event by using the following scales:

Attribution of Risk Categories:

Definite: Adverse event(s) will clearly be related to investigational agent(s) or other intervention

Probable: Adverse event(s) will likely be related to investigational agent(s)

Possible: Adverse event(s) may be related to investigational agent(s)

Unlikely: Adverse event(s) will doubtfully be related to investigational agent(s)

Unrelated: Adverse event(s) will clearly not be related to the investigational agents(s)

Grades of Risk:

0: No adverse event or within normal limits

1: Mild adverse event

2: Moderate adverse event

3: Severe adverse event resulting in hospitalization or prolongation of existing hospitalization, a persistent or significant disability/incapacity, or a congenital anomaly/birth defect

4: Life-threatening or disabling adverse event

5: Fatal adverse event

Serious adverse events (SAEs) include any untoward medical occurrence that at any dose results in death or the immediate risk of death, hospitalization or the prolonging of an existing hospitalization, persistent or significant disability/incapacity or a congenital anomaly/birth defect. Participants will be terminated from participation if the investigator feels that participants' health or well-being may be threatened by continuation in the study. Serious unanticipated adverse events will be reported within 48 hours to the Partners IRB. The principal investigator will evaluate the adverse event and determine whether the adverse event affects the Risk/Benefit ratio of the study and whether modifications to the protocol are required. In addition, he will conduct a review of all adverse events at least semi-annually, and he will evaluate the frequency and severity of the adverse events and determine if modifications to the protocol or consent form are required.

MONITORING AND QUALITY ASSURANCE

Describe the plan to be followed by the principal investigator/study staff to monitor and assure the validity and integrity of the data and adherence to the IRB-approved protocol. Specify who will be responsible for monitoring, and the planned frequency of monitoring. For example, specify who will review the accuracy and completeness of case report form entries, source documents, and informed consent.

NOTE: Regardless of monitoring plans by the sponsor or others, the principal investigator is ultimately responsible for ensuring that the study is conducted at his/her investigative site in accordance with the IRB-approved protocol, and applicable regulations and requirements of the IRB.

The research assistants will be responsible for day-to-day monitoring of the validity and integrity of the data. [name] will meet with the research assistants to discuss data monitoring on a monthly basis and will sample participant data folders monthly as well.

For guidance, refer to the following Partners policies:

Data and Safety Monitoring Plans and Quality Assurance

[https://partnershealthcare-public.sharepoint.com/ClinicalResearch/DSMP in Human Subjects Research.pdf](https://partnershealthcare-public.sharepoint.com/ClinicalResearch/DSMP%20in%20Human%20Subjects%20Research.pdf)

Reporting Unanticipated Problems (including Adverse Events)

[https://partnershealthcare-public.sharepoint.com/ClinicalResearch/Reporting Unanticipated Problems including Adverse Events.pdf](https://partnershealthcare-public.sharepoint.com/ClinicalResearch/Reporting%20Unanticipated%20Problems%20including%20Adverse%20Events.pdf)

PRIVACY AND CONFIDENTIALITY

Describe methods used to protect the privacy of subjects and maintain confidentiality of data collected. This typically includes such practices as substituting codes for names and/or medical record numbers; removing face sheets or other identifiers from completed surveys/questionnaires; proper disposal of printed computer data; limited access to study data; use of password-protected computer databases; training for research staff on the importance of confidentiality of data, and storing research records in a secure location.

NOTE: Additional measures, such as obtaining a Certificate of Confidentiality, should be considered and are strongly encouraged when the research involves the collection of sensitive data, such as sexual, criminal or illegal behaviors.

All data collected will be de-identified with participant ID numbers and used for research purposes only. Written records will be kept in a locked file cabinet in a locked office. They will be destroyed after 7 years. Computerized data files will also be de-identified with subject ID numbers and kept in a password protected file on a password protected computer.

SENDING SPECIMENS/DATA TO RESEARCH COLLABORATORS OUTSIDE PARTNERS

Specimens or data collected by Partners investigators will be sent to research collaborators outside Partners, indicate to whom specimens/data will be sent, what information will be sent, and whether the specimens/data will contain identifiers that could be used by the outside collaborators to link the specimens/data to individual subjects.

Not applicable.

Specifically address whether specimens/data will be stored at collaborating sites outside Partners for future use not described in the protocol. Include whether subjects can withdraw their specimens/data, and how they would do so. When appropriate, submit documentation of IRB approval from the recipient institution.

RECEIVING SPECIMENS/DATA FROM RESEARCH COLLABORATORS OUTSIDE PARTNERS

When specimens or data collected by research collaborators outside Partners will be sent to Partners investigators, indicate from where the specimens/data will be obtained and whether the specimens/data will contain identifiers that could be used by Partners investigators to link the specimens/data to individual subjects. When appropriate, submit documentation of IRB approval and a copy of the IRB-approved consent form from the institution where the specimens/data were collected.

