d.5. Neuropsychological Assessment. (see Appendix for description of assessments) We will use a brief battery of standard, well-known neuropsychological tests designed primarily to evaluate general intellectual capacity and executive/attentional functions. All test scoring will be completed blind to participants' clinical ratings. The WASI 4-subtest version (Vocabulary, Similarities, Block Design and Matrix Reasoning) is a reliable, brief assessment used to obtain IQ estimates (Wechsler 1981). The Rey Auditory Verbal Learning Test (RAVLT) assesses immediate memory span, new learning, susceptibility to interference, and recognition memory (Lezak et al. 2004). The Stroop Color Word Task challenges the ability to inhibit inappropriate responses and resist interference (Bush et al. 2003). The Multi-Source Interference Task (MSIT) has been shown to reliably and robustly activate cingulo-frontal-parietal circuitry associated with cognitive/attentional pathways (Bush and Shin, 2006). The Go/No Go Task is a task of inhibitory control (Menon et al. 2001).

Table D.1 Schedule of Measures

Baseline only

Physical examination

Structured Clinical Interview for
DSM-IV

Menstrual Cycle Info. (Women only)

Drug and Alcohol Use Questionnaire

Wechsler Abbreviated Scale of Intelligence

Tiffany QUS Brief form

Wisconsin Smoking Withdrawal Scale

Positive and Negative Affect Scales (PANAS)

Baseline and week 3

Tiffany QUS Brief form

Wisconsin Smoking Withdrawal Scale

Positive and Negative Affect Scales (PANAS)

Menstrual Cycle Info. (Women Only)

Baseline, weeks 10, 14, and 22

ECG

Rey Auditory Verbal Learning Test

Multi-Source Interference Task

Assessment (from the LIFE)

Quick Inventory of Depressive Symptomatology

Client Satisfaction Questionnaire-8

Laboratory tests^a

Stroop Color Word Test

Timeline Followback Functional

Risk Assessment Battery

Fagerstrom Test for Nicotine

Dependence

^aTests include urinalysis, electrolytes, complete blood count, & blood chemistries

Baseline and weekly

Daily Diary

Alveolar Carbon Monoxide (CO)

Adverse Events & Side Effects

Baseline and monthly

LIFE

Treatment Services Review

Urine pregnancy test

8.2. Data Analysis.

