a. For the main outcome measures acquired during treatment and post-treatment follow-up, the analytical approach will address the nature of the outcome (e.g., categorical vs. quantitative outcomes), as well as accommodate the within-individual correlation due to repeated assessments. In addition, the results from the given approach will be assessed for sensitivity to drop outs or missing data. The primary data analysis will be an intent-to-treat analysis, which includes all randomized participants. Of note, every attempt will be made to continue assessing participants even if they drop out of treatment. In addition, we will replicate all analyses with the completers only. The primary and secondary outcome variables are intended to explore various aspects of response to therapy and

to help define a clinically meaningful response. The primary outcome measures, 7-day point prevalence of abstinence, and expired CO, have been chosen for their ability to indicate daily use of cigarettes by relying on self-report of use.

Specifically, for assessing the effect of DCS on smoking patterns, we propose to use the generalized estimating equations (GEE) approach to longitudinal analysis, appropriately accounting for the positive correlation among the post-baseline repeated binary measures of 7-day abstinence within the same individual. The GEE approach incorporates all of the repeated assessments on an individual and provides a more powerful statistical analysis than does a cross-sectional analysis that focuses only on a single summary index. Specifically, we will fit logistic regression models for the repeated post-randomization binary measures of 7-day abstinence of the following form: $\text{logit}(p) = \beta_0 + \beta_1 \text{trt}$, where trt (treatment)=1 if randomized to DCS and trt=0 otherwise, and p denotes the probability of 7-day abstinence.

The logistic regression model will be fit using the GEE approach (as implemented in PROC GENMOD in SAS) to account for correlation among repeated assessments of the same individual. The logistic regression analyses will also adjust for the stratification factor used in the randomization of patients. The GEE analysis accounts for this within-subject correlation, and the resulting estimated β_1 , when exponentiated, provides an estimate of the treatment effect expressed as an odds ratio, comparing the DCS group to the placebo group. The effect of DCS on 7-day abstinence will be assessed by testing $H_0: \beta_1=0$.

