A relatively similar analytic approach will be used to assess the effect of DCS on changes in expired CO assessments. A linear mixed effects model will be used to assess changes in CO during treatment and at post-treatment follow-up. The linear mixed effects model will include the effects of treatment group, time and the baseline measure of CO; the inclusion of random effects accounts for the correlation among the 12 post-baseline CO measurements (1-per week during 10 weeks of treatment, plus week 14 and 22). We will adjust for the dose of NRT by including dose as an additional covariate in the linear mixed effects model analysis of the treatment comparison (DCS vs. placebo). The linear mixed effects model includes random intercepts and random slopes for time to appropriately account for correlation among repeated measures of CO and heterogeneity of variance over time; the model will be fit using PROC MIXED in SAS.

Analyses of secondary outcomes will focus on assessing the effect of DCS on neuropsychological assessments. For example, linear mixed effects models will also be used to analyze quantitative/continuous neuropsychological outcomes (e.g., MSIT response accuracy and times), with appropriate transformation (e.g., log transformation) of the outcome as necessary. To examine the effect of DCS on changes in neuropsychological performance during treatment, the linear mixed effects model will include the effects of treatment condition and the baseline measure of the neuropsychological outcome. Additional analyses of secondary outcomes will focus on the number of days of cigarette smoking during treatment and post-treatment follow-up. Frequency of days of cigarette use will be analyzed via a log-linear (or Poisson) regression model, controlling for pre-treatment frequency of days of cigarette use. Although log-linear regression methods are considered appropriate for the analysis of count or frequency data, in many biomedical applications, count data have variability that far exceeds that predicted by the Poisson distribution; we expect that days of cigarette use will not be an exception. This phenomenon, known as overdispersion, will be accounted for in the planned regression analysis through the inclusion of a

dispersion parameter. The log-linear regression analyses will be fit using PROC GENMOD in SAS.

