b. Missing Data and Dropout. With repeated assessments, missing data are inevitable. Incomplete data pose 2 concerns for inference: bias and efficiency. We will use statistical methods (GEE and linear mixed effects models) that incorporate partially observed data on participants who drop out. We will provide detailed descriptions of the patterns of missing data and assess the sensitivity of results to different assumptions about the mechanism by which data are missing. For example, pattern-mixture models can be used to assess the sensitivity of results to informative dropout or missing data. [name], our biostatistician consultant, is an expert in handling missing data in longitudinal studies (Fitzmaurice et al. 2004).

c. Sample Size and Power. We plan to randomize 20 participants per group for a total of 40 subjects. This sample size will provide a reasonable estimate regarding the effect size for a subsequent larger trial. With a total of 40 participants, and assuming a Type-I error level (alpha-level) of 0.05 (two-sided), a 7-day abstinence prevalence of 25% in the placebo group, the study would have approximately 80% power to detect medium effect sizes, corresponding to risk ratios of 2.3-2.6 (as the within-participant correlations ranges from 0.3-0.7). For example, with moderate within-participant correlation ($\rho=0.5$), the study would have 80% power to detect a risk ratio of 2.48.

For studies involving treatment or diagnosis, provide information about standard of care at Partners (e.g., BWH, MGH) and indicate how the study procedures differ from standard care. Provide information on available alternative treatments, procedures, or methods of diagnosis.

The standard of care for nicotine dependence is psychotherapy and/or medication; our treatment attempts to strengthen the best available treatment by enhancing the behavioral intervention.

Describe how risks to subjects are minimized, for example, by using procedures which are consistent with sound research design and which do not unnecessarily expose subjects to risk or by using procedures already being performed on the subject for diagnostic or treatment purposes.

Care will be taken to minimize risk. In addition to carefully screening prior to enrollment, we have weekly visits during which we will carefully monitor response to medication or placebo with respect to side effects and changes in mood.

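### The secondary smoking-days count model has no observed-days offset, so unequal observed time between arms could bias its rate ratio (low priority, cheap to fix)

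*Combined protocol and SAP*

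**What the plan says.** The outcome is defined in 8.2 Data Analysis, part a: "Additional analyses of secondary outcomes will focus on the number of days of cigarette smoking during treatment and post-treatment follow-up". It is to be "analyzed via a log-linear (or Poisson) regression model, controlling for pre-treatment frequency of days of cigarette use". The same paragraph adds a dispersion parameter for overdispersion and names PROC GENMOD. Both periods are named, and other sections fix their length: 10 weeks of treatment, then follow-up to week 22. The paragraph does not state an offset or denominator, whether the two periods form one total or two, or how a day without data is counted. It also does not carry over the adjustment for the randomisation stratum (baseline CO 10-20 or >20 ppm) that part a states for the logistic analyses.

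Several provisions bear on incomplete data:

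- Part b, Missing Data and Dropout: "We will use statistical methods (GEE and linear mixed effects models) that incorporate partially observed data on participants who drop out". It also promises to "assess the sensitivity of results to different assumptions about the mechanism by which data are missing".
- Part a: "every attempt will be made to continue assessing participants even if they drop out of treatment", and "we will replicate all analyses with the completers only".
- Section d.2 plans Timeline Followback at the weekly visits, alongside the daily diary. Table D.1 lists Timeline Followback under "Baseline, weeks 10, 14, and 22".

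**The concern.** A count depends on how long it is collected. In a log-linear model without an offset, a participant observed for 28 days and one observed for 70 days are compared as if both had the same opportunity to record smoking days. If one arm loses more observed time, its mean count falls for a reason unrelated to treatment. The dispersion parameter widens the standard error but does not move the ratio.

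Unequal observation is possible here. Under Safety Monitoring, participants taken off medication for an unexplained abnormality are followed at follow-up assessment visits only, which might end weekly collection for them. This is a possible route, not an established one.

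The result can also depend on the rule for unobserved days. Totals over observed days favour the arm with more loss, whereas counting unobserved days as smoking leaves that arm the same or worse. With the rule open, the choice could be made after the data are seen. At stake is one secondary estimate in a pilot meant to inform the effect size for a larger trial.

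**Working it through.** The plan gives no figure for this outcome. Its power statement concerns 7-day abstinence and is not touched by this point.

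**Inputs from the documents:** 20 participants per arm and 25% abstinence on placebo (Sample Size and Power); treatment 10 × 7 = 70 days; follow-up (22 − 10) × 7 = 84 days; total 154 days.

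**Assumptions, because no dropout rate is given:** no true effect; 25% abstinent and 75% daily smokers in both arms; one arm fully observed; a fraction d = 0.1, 0.2 or 0.3 (2, 4 or 6 of 20) of the other arm lost at day 28 with no later data. These losses are near upper bounds. In pattern A all those lost are smokers; in pattern B loss is unrelated to smoking. The baseline covariate is left out.

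**Formulas for the 70-day window.** With treatment as the only term, the fitted ratio is the ratio of mean counts or, with an offset, of smoking days per observed day.

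- Full-data mean: 0.75 × 70 = 52.5 days.
- Mean observed days in the arm with loss: 70 − 42d = 65.8, 61.6, 57.4.
- A, no offset: (0.75 − d) × 70 + 28d = 48.3, 44.1, 39.9; divided by 52.5 = 0.92, 0.84, 0.76.
- A, with offset: (48.3/65.8)/0.75, (44.1/61.6)/0.75, (39.9/57.4)/0.75 = 0.98, 0.95, 0.93.
- A, completers: ((0.75 − d)/(1 − d))/0.75 = 0.96, 0.92, 0.86.
- B, no offset: 0.75 × (70 − 42d) = 49.35, 46.2, 43.05; divided by 52.5 = 0.94, 0.88, 0.82.
- Unobserved days as smoking: (count + 42d)/52.5.
- Half of those lost recovered later: replace d by d/2.
- One combined 154-day total: A ((0.75 − d) × 154 + 28d)/115.5; B (154 − 126d)/154.

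| Analysis | Pattern A | Pattern B |
|---|---|---|
| No offset | 0.92, 0.84, 0.76 | 0.94, 0.88, 0.82 |
| Offset for observed days | 0.98, 0.95, 0.93 | 1.00 throughout |
| Completers only | 0.96, 0.92, 0.86 | 1.00 throughout |
| Unobserved days as smoking | 1.00 throughout | 1.02, 1.04, 1.06 |
| No offset, half recovered | 0.96, 0.92, 0.88 | 0.97, 0.94, 0.91 |
| No offset, combined 154 days | 0.89, 0.78, 0.67 | 0.92, 0.84, 0.75 |

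**Precision.** Overdispersed Poisson fits (Pearson scale, 20 against 20) to pattern A without an offset give standard errors of the log ratio of 0.196, 0.204 and 0.212. The log biases are −0.083, −0.174 and −0.274, which is 0.43, 0.85 and 1.29 standard errors. The 95% intervals are 0.63-1.35, 0.56-1.25 and 0.50-1.15. The largest bias corresponds to p = 0.20.

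**Check by simulation.** This used varying smoking rates averaging 60% of days, dropout at a uniform random time unrelated to smoking, 20 per arm and no true effect.

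- Equal 20% dropout: ratio 1.00 without an offset; rejection at nominal 5% was 5.1%.
- 40% against 20%: 0.88 without an offset (rejection 10.2%), 1.00 with one, and 1.06 with unobserved days as smoking.
- 60% against 20%: 0.77 without an offset (rejection 26.2%) and 1.00 with one.
- With the offset, rejection was 6.0-7.3% across all the dropout settings run.

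**The case against.** The case for leaving this alone is substantial.

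- **Several conditions must coincide.** Days must be totalled over observed time, loss must differ by arm, and missed days must stay unrecovered. The documents neither state the first nor give a reason to expect the second, and equal loss gives 1.00. This stands, and it makes the size unknown.
- **Other readings are open.** Part a also speaks of the frequency of days, weekly Timeline Followback could supply weekly counts, and PROC GENMOD is the procedure named for the GEE analysis. With proportions or weekly counts, unequal time alone causes no bias. Under selective loss, weekly counts depend on the working correlation: single simulated runs of pattern A gave 1.01, 1.00, 0.99 with an exchangeable structure and 0.97, 0.96, 0.93 with independence. Part a states neither weekly counts nor GEE for this outcome, so the gap remains.
- **Safeguards exist.** A reader might infer that the plan leaves missing data on this outcome unaddressed. That goes too far: the sensitivity work is not limited by outcome, and the completers-only replication covers all analyses and gives 1.00 in pattern B. It still gives 0.86 in the worst case of pattern A, and the methods named for partial data do not include this count model.
- **The offset is not a complete cure.** It leaves 0.93 in the worst case of pattern A and is undefined for a participant with no observed days. This also stands.

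**Conclusion.** The omission is real and the bias is conditional. If smoking days are totalled per person over observed time and observed time differs by arm, the model as written pulls the ratio toward fewer smoking days in the arm observed for less time. In the 70-day illustrations the ratio without an offset runs from 0.94 to 0.76 under no true effect. The bias stays within the 95% half-width at this sample size, although it exceeds one standard error in the most severe case. Every magnitude rests on assumed loss.

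A reader might infer that the plan sets no time window, or that its result will favour DCS. The documents support neither. The periods are named, and only their pooling is open. Nothing indicates which arm, if either, would lose more time. Both primary analyses are unaffected. This is an additional secondary analysis in a 40-person pilot, so the point is a cheap, low-priority improvement. The missing CO stratum is a separate minor matter whose effect was not quantified.

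**What to change.** Keep the planned overdispersed log-linear model and specify the following:

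1. Add log(days with Timeline Followback data) as an offset. Use the diary only for days that Timeline Followback does not cover, so that one source has priority.
2. Analyse treatment (days 1-70) and follow-up (days 71-154) separately, and report observed days by arm for each.
3. Run one sensitivity analysis that counts every unobserved day as a smoking day over the full window. It keeps participants with zero observed days, who cannot enter the offset model.
4. Include the CO randomisation stratum as a covariate, as the logistic analyses already do.

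The cost is a few sentences of SAP text, an OFFSET= term and one covariate in the same PROC GENMOD call, separate fits for the two periods, and one extra sensitivity analysis. No new data are needed.

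Two downsides should be stated in the plan. The offset does not remove bias from selective loss of smokers, and participants with zero observed days leave the main model. Counting unobserved days as smoking overstates smoking when abstainers are lost (1.02-1.06 in pattern B), so it should stay a sensitivity analysis.
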